8.6.2.8 Monthly SBM Response

A monthly responder is defined as a subject who is a weekly responder for 3 of 4 weeks per month. A weekly responder is defined as a subject who has a frequency rate of ≥ 3 SBMs/week and an increase from baseline of ≥ 1 SBM/week for that week. Analyses of the frequency rates of SBMs per month will be performed using the van Elteren test, stratified by pooled centres.

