2.2.2 Efficacy

The efficacy endpoints are as follows:

- Overall and monthly changes from baseline in BM and SBM frequency rate
- Overall and monthly assessments of the average degree of, and changes from baseline in:
 - Stool consistency of SBMs
 - Straining associated with SBMs
 - Abdominal pain associated with SBMs
 - Constipation severity
- Monthly SBM Response
 - A monthly responder is defined as a subject who is a weekly responder for 3 of 4 weeks per month.

- A weekly responder is defined as a subject who has a frequency rate of ≥ 3 SBMs/week and an increase from baseline of ≥ 1 SBM/week for that week.
- Overall and monthly assessment of average treatment effectiveness rating
- Overall Health-related quality of life (PedsQL™)
- Overall and monthly change from baseline in incontinence episodes frequency (analysis performed for subset of subjects presenting with incontinence at baseline)
- Overall and monthly change from baseline in the production of large diameter stool (a stool that clogs the toilet) frequency
- Overall and monthly change from baseline in frequency of faecal impaction
- Overall and monthly change from baseline in proportion of BMs and SBMs in toilet overall
- Overall and monthly change from baseline in frequency of retentive posturing or excessive volitional stool retention

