8.6.2 Efficacy Endpoints

8.6.2.1 Overall and Monthly Change from Baseline in BM and SBM Frequency

Changes from baseline in BM and SBM frequency will be analysed overall, and at each month from Months 1 through Month 9. A month is defined as a 4-week period; e.g., Month 1 is Weeks 1-4; Month 2 is Weeks 5-8; Month 3 is Weeks 9-12. The SBM frequency rate per week will be computed as specified in [Section 8.6.2.1](#). The analyses of the months will utilize the same methods as those used in the analysis of weeks.

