8.6.2.7 Overall and Monthly Change from Baseline in Constipation Signs and Symptoms

Mean changes from baseline will be generated based on subject reported data as to the degree of:

- Straining associated with SBMs;
- Stool consistency of SBMs;
- Abdominal pain associated with SBMs; and
- Constipation severity.

The following rating scales will be used:

Stool consistency: Modified Bristol Stool Form Scale (5-point scale);

Bowel straining: 0=Not at all, 1=A little, 2=Some, 3=Quite a bit, 4=Extremely

Constipation severity and abdominal pain: 0=Absent, 1=Mild, 2=Moderate, 3=Severe, 4=Very severe.

The overall change from baseline will be calculated as the baseline value subtracted from the average of all diary ratings, where the baseline value will represent the average rating during the 2-week screening period of the previous study (SAG/0211PFC-1131). The change from baseline for a week (7-day period) or month (4-week period) will also be calculated as the baseline value subtracted from the average of all diary ratings during a week or month.

Stool Consistency

The analysis of stool consistency will focus on consistency assessments associated with SBMs. The average stool consistency rating will be calculated for each month (4-week period), excluding measurements recorded within 24 hours after rescue medication intake.

Analyses will be based on the change from baseline, where the baseline value will represent the average stool consistency rating from all SBMs during the 2-week screening period of the previous study (SAG/0211PFC-1131). The van Elteren test using the change from baseline stratified by pool centre and stratified by study for the pooled group will be used.

Straining

Bowel straining will be analysed in a method similar to stool consistency.

Constipation Severity

The changes from baseline in mean constipation severity ratings at each month during Months 1 through 9 will be analysed. The change from baseline will be calculated as the baseline value subtracted from the average of all diary ratings during the given month. For these daily diary assessments, each month will be defined by 4-week intervals beginning with the day of the first dose of study medication (Day 1). For example, Month 1 will start with the daily assessment on Day 1 and end with the daily assessment on Day 29 (Week 4), Month 2 will start with the daily assessment on Day 30 and end with the daily assessment on Day 57 (Week

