8), and Month 3 will start with the daily assessment on Day 58 and end with the daily assessment on Day 85 (Week 12). Each week will be defined by 7-day intervals beginning with the day of the first dose of study medication (Day 1).

The van Elteren test using the change from baseline stratified by pooled centre for the individual studies and stratified by study for the pooled group will be used.

Abdominal Pain

Abdominal pain will be analysed similarly to constipation severity. Summary tables for the monthly change from baseline will also be presented.

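### Monthly SBM Response is defined as yes/no, but the only analysis under its heading is a rank test of SBM frequency; separately, the month cuts for constipation severity break the plan's own four-week rule by one day

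*Combined protocol and SAP*

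**What the plan says.** **Response.** Section 8.6.2.8 (Monthly SBM Response) gives a two-level definition. "A monthly responder is defined as a subject who is a weekly responder for 3 of 4 weeks per month". A weekly responder needs at least 3 SBMs in the week and "an increase from baseline of ≥ 1 SBM/week for that week". Both levels are yes/no. The section then closes with its only analysis statement: "Analyses of the frequency rates of SBMs per month will be performed using the van Elteren test, stratified by pooled centres".

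**Frequency.** SBM frequency is listed as an endpoint in its own right in section 2.2.2: "Overall and monthly changes from baseline in BM and SBM frequency rate". Its analysis section, 8.6.2.1, names no test. It cites itself for how the weekly rate is computed, and says months are handled by the methods used for weeks, which the protocol does not describe.

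**Months.** Section 8.6.2.1 states: "A month is defined as a 4-week period; e.g., Month 1 is Weeks 1-4". Section 8.6.2.7, under Constipation Severity, also builds months from 4-week intervals starting on Day 1 and adds: "Each week will be defined by 7-day intervals beginning with the day of the first dose of study medication (Day 1". Its worked example, however, says "Month 1 will start with the daily assessment on Day 1 and end with the daily assessment on Day 29 (Week 4", and continues with Month 2 as Days 30 to 57 and Month 3 as Days 58 to 85. Abdominal pain is to be handled like constipation severity. Stool consistency and straining refer only to a 4-week period.

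**The concern.** The analysis sentence in 8.6.2.8 does not concern the variable that the section defines. A programmer following it would produce a rank comparison of SBM rates under the title of monthly response, and would find no instruction for the responder proportion. That proportion is the endpoint that describes whether benefit is sustained from month to month over 36 weeks. Meanwhile the frequency endpoint would have no named test in its own section.

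The month cuts are a separate problem. Two statements in the same subsection cannot both be programmed: either a month is four 7-day weeks from Day 1, or Month 1 ends on Day 29. If the example is followed for severity and abdominal pain, and the 4-week rule for everything else from the diary, the same month label covers slightly different days in different tables.

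**Working it through.** **1. Can SBM frequency stand in for response?**

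Inputs: the weekly rule in 8.6.2.8; an assumed baseline of 1 SBM/week; the monthly rule read as at least 3 of 4 weeks.

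- Child A, weekly counts 3, 3, 3, 0. Rate = 9/4 = 2.25/week. Three weeks have a count of at least 3 and a rise of 3 - 1 = 2, so three weeks qualify: responder.
- Child B, weekly counts 9, 2, 2, 2. Rate = 15/4 = 3.75/week. Only one week qualifies: non-responder.

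Ranked on frequency, B stands above A; on response the order is reversed. The baseline is the same for both, so ranking on change from baseline gives the same reversal.

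A constructed simulation shows how far the two can part. Assumptions: 200 children per group, four weeks, both groups with a mean of 3.5 SBMs/week, baseline 1, counts Poisson in one group and binomial(7, 0.5) in the other, 2,000 runs. An unstratified rank test stood in for van Elteren.

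| Quantity | Poisson group | Binomial group |
|---|---|---|
| Mean SBMs/week | 3.50 | 3.50 |
| Monthly responders | 61.6% | 77.7% |

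The rank test on frequency rejected in 6% of runs and a chi-square test on responders in 95%. The inputs were chosen to separate the two variables. The result shows that they can disagree, not that they would here.

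**2. What does three of four mean?**

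The phrase "a weekly responder for 3 of 4 weeks per month" does not say at least. With an assumed weekly response probability p, independent between weeks, exactly three has probability 4p³(1-p), and at least three adds p⁴.

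| p | Exactly 3 | At least 3 |
|---|---|---|
| 0.5 | 0.250 | 0.312 |
| 0.7 | 0.412 | 0.652 |
| 0.8 | 0.410 | 0.819 |

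**3. Month windows.**

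The plan's figure is Day 29 as the end of Month 1, labelled Week 4. With weeks of 7 days from Day 1, Week w ends on Day 7w, so Week 4 ends on Day 28. Day 29 is 7 × 4 + 1. Counting elapsed days does not rescue it: Days 2 to 29 are 28 days, but the text starts Month 1 on Day 1.

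| Month | As written | Length | By the week rule, Days 28(k-1)+1 to 28k | Days shared |
|---|---|---|---|---|
| 1 | 1-29 | 29 | 1-28 | 28 |
| 2 | 30-57 | 28 | 29-56 | 27 |
| 3 | 58-85 | 28 | 57-84 | 27 |

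Day d falls in week floor((d-1)/7) + 1, so Days 29, 57 and 85 fall in Weeks 5, 9 and 13. If the pattern continued, Month 9 would end on Day 29 + 8 × 28 = 253, against 9 × 28 = 252. The example stops at Month 3, so this last step is an extrapolation.

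Size: with complete diaries, Day 29 carries 1/29 = 3.4% of a child's Month 1 mean. On the 0-4 scale, one added rating moves that mean by at most 4/29 = 0.14. In later months one day is swapped for another, moving the mean by at most 4/28 = 0.14. Both are extremes for a single child.

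**The case against.** The strongest reply has four parts.

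- **The sentence is only misplaced.** It does not claim to test response through frequency; it describes another variable under the wrong heading. The synopsis already promises counts and percentages for categorical variables. This stands, and it shapes the remedy: a reader might infer that the sentence is redundant and should be struck out, but it is the only test named for SBM frequency, so deleting it would leave that endpoint without a method.
- **Detail is deferred to the SAP.** The synopsis leaves detailed methods to the SAP, and section 8.6.1.1 leaves missing data to it. No separate SAP text on this endpoint is in the documents available. A reader might infer that responder percentages will rest on observed cases and rise as children who do poorly leave, since lack of efficacy is a listed withdrawal reason. The documents do not support that: they state no observed-case denominator, and they base efficacy on the mITT population. The handling of children who leave is unknown, not shown to be wrong.
- **Exactly three is a strained reading.** It would count a child who responds in all four weeks as a failure. At least three is almost certainly meant, so this is a wording clarification, not an analysis error.
- **The Day 29 cut is a labelling slip with little effect.** Days 29, 85 and 253 are the Week 4, 12 and 36 visit days in the Schedule of Evaluations, which probably explains the example. A reader might infer that symptom and frequency results for a month cannot be lined up, but the two definitions share 28 of 29 days in Month 1 and 27 of 28 in Months 2 and 3. The example also covers only constipation severity and, by reference, abdominal pain.

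None of this removes the two contradictions. A later SAP may add a responder analysis, but 8.6.2.8 would still name the wrong variable, and the two month rules in 8.6.2.7 would still conflict.

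**Conclusion.** Two errors stand on the text itself, without assumptions. Section 8.6.2.8 attaches to a binary endpoint an analysis of a different variable, while the section for that variable names no test. Section 8.6.2.7 ends its example months on Days 29, 57 and 85, although its own rule gives Days 28, 56 and 84.

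The first matters more, because the responder endpoint lacks an inferential method and frequency can order children differently from response. How often that would happen here is not known; the worked children and the simulation rest on assumed baselines and count distributions. The second is minor in numbers: one extra rating in Month 1 and a one-day shift afterwards.

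Both concern non-primary efficacy endpoints in a non-randomised study whose primary objective is safety. They should be corrected before database lock, but they do not threaten the study's main conclusions.

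**What to change.** - **8.6.2.1:** move the van Elteren sentence here, so that SBM frequency has its named test, and replace the self-reference with the actual computation of the weekly rate.
- **8.6.2.8:** define the monthly responder as a weekly responder in at least 3 of the 4 weeks. Analyse the responder indicator itself: the proportion of responders in each month in the mITT population, with a 95% CI. If groups are compared, add a stratified test for binary data, such as Cochran-Mantel-Haenszel by pooled centre. Point to the SAP section that says how children who have left are counted.
- **8.6.2.7:** set Month k to Days 28(k-1)+1 to 28k for all diary endpoints (Month 1 = Days 1-28, Month 9 = Days 225-252) and correct the example.
- **After Day 252:** state what happens to later ratings. The End-of-Treatment Visit is on Day 253 (+3 days in the schedule) and section 5.5 places the last dose on that day, so such ratings can exist. One option is to leave them out of Month 9 and keep them in the overall average.

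The cost is wording and window programming. No new data, visits or subjects are needed.

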8.6.2.9 Treatment Effectiveness

Measurements of treatment effectiveness will be collected via the diary at weekly intervals as well as overall using the following scale: 0 = Not at all effective, 1 = A little bit effective, 2 = Moderately effective, 3 = Quite a bit effective, 4 = Extremely effective.

8.6.2.10 Health-related Quality of Life

Health-related quality of life will be measured using the PedsQL™ questionnaire.

The PedsQL™ questionnaire has 4 subscales: physical functioning, emotional functioning, social functioning, and school functioning; in addition, there is a total score. Summary evaluations of response for every domain and total score at each timepoint will be provided by treatment arm. For each subscale and for the total score, the change from baseline at each visit will be analysed.

8.7 Data Quality Assurance

Steps to be taken to assure the accuracy and reliability of data include the selection of qualified Investigators and appropriate study sites, review of protocol procedures with the Investigator and associated personnel prior to the study, and periodic monitoring visits by the Sponsor or designee. Compliance will be achieved through a combination of study specific audits of investigational sites and audits at regular intervals of the Sponsor's systems for data handling, analysis, and reporting. eCRFs will be reviewed for accuracy and completeness by the Sponsor or designee during on-site monitoring visits and any discrepancies will be resolved with the Investigator or designees, as appropriate. The data will be entered into the clinical study database and verified for accuracy.

This study will be organised, performed, and reported in compliance with the Sponsor's Standard Operating Procedures, protocols and working practice documents, and the requirements of national and international GCP guidelines.

8.8 Data Collection

Original source data will be collected via source documents. Final data for this study will be collected using electronic case report forms (eCRFs). Data must be entered onto the eCRFs in English. All eCRFs must be completed in a timely manner before the Sponsor or designee performs a monitoring visit. The Principal Investigator will be required to electronically sign the eCRFs casebook for each subject. Laboratory reports must be reviewed, signed, and dated by an appropriate Investigator and filed with the source documents. Any laboratory findings out of the normal range should indicate the clinical significance (clinically significant [CS] or not-clinically significant [NCS]) of the results on both the source document and the corresponding eCRF.

The eCRFs are to be completed as soon as possible from the time of the subject's visit, with the exception of results of tests performed outside the Investigator's office, so that they always reflect the latest observations on the subjects participating in the study.

All eCRF corrections are to be made or reviewed by the Investigator or other authorized study site personnel.

Automatically generated queries will be answered by site personnel during the eCRF completion process.

The dates of the monitoring visits will be recorded by the monitor in a study site visit log to be kept at the site. The first post initiation visit will usually be made as soon as possible after enrolment has begun. At these visits, the monitor will compare the data entered into the eCRFs with the hospital or clinic records (source documents). Source documentation must be available to substantiate proper informed consent procedures, adherence to protocol procedures, adequate reporting and follow-up of AEs, administration of concomitant medication, medication receipt/dispensing/return records, and study medication administration information. Specific items required as source documents will be reviewed with the Investigator prior to the study. Findings from this review of eCRFs and source documents will be discussed with the Investigator. The Sponsor expects that, during monitoring visits, the Investigator and study coordinator, will be available, the original source documentation, regardless of media, will be available, and a suitable environment will be provided for review of study-related documents.

9. SPONSOR'S AND INVESTIGATOR'S RESPONSIBILITIES

This study will be conducted in accordance with current applicable regulations, International Conference on Harmonisation (ICH), European Union (EU) Directive 2001/20/EC¹⁷ and local ethical and legal requirements.

9.1 Sponsor's Responsibilities

9.1.1 GCP Compliance

The Sponsor and any third party to whom aspects of the study management or monitoring have been delegated will undertake their roles for this study in compliance with all applicable regulations, ICH GCP Guideline E6¹⁴ and EU Directive 2001/20/EC.¹⁷

Visits to Investigator sites will be conducted by representatives of the Sponsor to inspect study data, subjects' medical records and CRFs in accordance with current GCP and the respective local and national government regulations and guidelines. Records and data may additionally be reviewed by auditors, interested commercial parties or by regulatory authorities.

9.1.2 Regulatory Approval

The Sponsor will ensure that Local Regulatory Authority requirements are met before the start of the study. The Sponsor (or a nominated designee) will be responsible for the preparation, submission and confirmation of receipt of any Regulatory Authority approvals required prior to release of investigational product for shipment to the study site.

9.1.3 Indemnity/liability and Insurance

Sponsor will adhere to the recommendations of the Association of British Pharmaceutical Industry (ABPI) Guidelines. If appropriate, a copy of the Indemnity document will be supplied to the Investigator before study initiation.

Sponsor will ensure that suitable insurance cover is in place prior to the start of the study.

9.1.4 Protocol Management

All protocols and amendments will be prepared by The Sponsor. If it becomes necessary to issue a protocol amendment during the course of the study, the Sponsor will notify the Investigators and collect documented Investigator Agreement to the amendment.

9.1.5 End of Trial Notification

With respect to investigational sites within the EU, the Sponsor will submit an end of trial notification to individual Member States and IECs within 90 days of the end of the trial in accordance with EU Directive 2001/20/EC.¹⁷

The end of trial notification should be made when:

- the trial ends in the territory of the member state(s) concerned; and

- the complete trial has ended in all participating centres in all countries within and outside the EU.

For the purposes of this notification, the end of the complete trial will be defined as the last subject/last visit in all participating centres in all countries within and outside the EU and the end of trial in a member state will be defined as the last subject last visit in that member state.

However, if recruitment into the trial as a whole is on-going and there is a possibility that further subjects may be recruited into the trial in a member state where there are currently no active subjects, the end of trial notification for that member state will be deferred until it is certain that no further subjects will be recruited into the study in that member state.

9.1.6 Submission of Summary of Clinical Study Report to Competent Authorities of Concerned Member States and IECs

The Sponsor will provide a summary of the Clinical Study Report within one year of the end of the complete trial to the competent authority of the concerned Member State(s) as required by the regulatory requirement(s) and to comply with the Community guideline on Good Clinical practice. The Sponsor will provide the IECs with a copy of the same summary.

9.2 Investigator's Responsibilities

9.2.1 GCP Compliance

The Investigator must undertake to perform the study in accordance with ICH GCP Guideline E6¹⁴, EU Directive 2001/20/EC¹⁷, and the applicable regulatory requirements. A copy of the guidelines will be available in the Investigator Site File.

It is the Investigator's responsibility to ensure that adequate time and appropriate resources are available at the study site prior to commitment to participate in this study. The Investigator should also be able to estimate or demonstrate a potential for recruiting the required number of suitable subjects within the agreed recruitment period.

The Investigator will maintain a list of appropriately qualified persons to whom the Investigator has delegated significant trial-related tasks. An up-to-date copy of the *curriculum vitae* for the Investigator, Sub-investigator(s) and essential study staff will be provided to the Sponsor (or designee) before starting the study.

If the subject has a primary physician the Investigator should, with the subject's consent, inform them of the subject's participation in the trial.

A Coordinating Principal Investigator will be appointed as soon as possible, but prior to the end of the study, to review the final Clinical Study Report for multicentre studies. Agreement with the final Clinical Study Report will be documented by the signed and dated signature of the Coordinating Principal Investigator (multicentre study), in compliance with Directive 2001/83/EC and ICH E3.¹⁸

